13.4.2. Duration of Exposure and Compliance

Trial drug administration (i.e., amount administered) will be summarized in terms of each patient's mean, mode, and final dose, and in terms of duration of exposure. Descriptive statistics for these quantities, including the mean, median, SD, minimum, maximum, and quartiles, will be provided by treatment and part.

13.4.3. Efficacy Analyses

13.4.3.1. Primary Analysis

The mean IV GIR in the last 12 hours of each treatment period during Part 1 will be analyzed for the FAS and PP populations. The hypothesis:

$$H_1: \text{Reduction in weighted mean IV GIR}_{\text{dasiglucagon}} = \text{Reduction in weighted mean IV GIR}_{\text{placebo}}$$

will be based the last 12 hours of each treatment period, calculated as a weighted mean across the 12 hours, taking the actual time periods between the measurements into account (corresponding to calculating the area under the curve [AUC] and dividing by the length of the time period, i.e., weighted mean IV GIR). The IV GIR endpoint is expressed as glucose in mg/kg/min, i.e., data reported from different concentrations of the glucose used for infusion will be transformed to this standardized unit prior to analysis.

The primary analysis is defined by the estimand based on the treatment policy (de-facto) strategy, where the actual GIR measurement reported irrespective of adherence to treatment or

use of subsequent therapy is used. The reduction in weighted mean IV GIR between placebo and dasiglucagon will be estimated.

The weighted mean IV GIR will be analyzed using a mixed-model regression approach, with treatment and period as fixed effects and patient as a random effect. The 2-sided 95% confidence interval (CI) for the treatment difference will be calculated from the mixed regression model.

Missing data will be imputed using the following methodology: if the weighted mean IV GIR is missing for the placebo period, it will be imputed using the baseline weighted mean IV GIR; if the weighted mean IV GIR is missing for the dasiglucagon period, it will be imputed using the placebo-weighted mean IV GIR for that patient. As a sensitivity analysis, the primary endpoint will be re-analyzed as follows: 1) using only complete cases (i.e., weighted mean IV GIR is non-missing for both placebo and dasiglucagon) and 2) imputing missing weighted mean IV GIR using the baseline weighted mean IV GIR and 3) imputing missing dasiglucagon values during one period with the placebo value for that patient and imputing missing placebo values with the mean values of placebo patients for that period..

13.4.3.2. Key Secondary Analyses

The hypothesis:

H_{12} : Total amount (g) of carbohydrates administered (regardless of the route) per day
dasiglucagon = total amount (g) of carbohydrates administered (regardless of the route)
per day placebo

between the 2 treatment groups will be analyzed by using a mixed-model regression approach, with treatment and period as fixed effects and patient as a random effect. The total amount (g) of carbohydrates administered (regardless of the route) per day is the sum of the last 48 hours of each period in Part 1.

For the key secondary endpoint, 2-sided 95% CIs for the treatment differences will be estimated from the mixed-model. Missing dasiglucagon values during one period will be imputed with the placebo value for that patient and missing placebo values will be imputed with the mean values of placebo patients for that period. In addition, a sensitivity analysis will be performed using complete cases.

13.4.3.3. Secondary and Other Efficacy Analyses

Part 1

A mixed-model regression approach will be used to analyze the weighted mean IV GIR over 48-hour treatment period during Part 1 (dasiglucagon or placebo administration) similar to the primary analysis for the primary endpoint.

A generalized estimating equation (GEE) method with a logit link function will be used to analyze the weighted mean IV GIR below 10 mg/kg/min in the last 12 hours of each treatment period during Part 1 (yes/no) (dasiglucagon or placebo administration) to account for repeated observations in patients. In case of non-convergence, a Mc Nemar test will be used.

No sensitivity analysis will be used on these endpoints.

Part 2

Due to the potential impact of pancreatectomy on the secondary endpoints during Part 2, any endpoint assessment after pancreatectomy will not be included in the primary analyses

(endpoints set to missing after pancreatectomy). Sensitivity analyses will be run on those endpoints including all assessments in the descriptive analyses.

For Part 2 efficacy endpoints, continuous and categorical endpoints will be presented using summary statistics or frequencies, respectively; no formal testing will be performed. For the time to complete weaning off IV GIR, the time to actual hospital discharge and the time to pancreatic surgery, Kaplan-Meier curves will be produced.

13.4.4. Safety and Tolerability Analyses

Safety analyses will be conducted using data from the Safety Population (as defined in Section 13.3). Safety assessments will include the evaluation of AEs; clinical laboratory assessments (hematology, biochemistry, and ADAs); vital signs, physical examinations; ECGs, echocardiography, and local tolerability issues. No formal inferential analyses will be conducted for safety variables, unless otherwise noted.

Baseline is defined as the last nonmissing assessment before the first exposure to trial drug in the trial.

All safety analyses will be summarized by treatment received within treatment period and part and by trial visit, if applicable.

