6.3.6. Anticipated Risks of Dasiglucagon in the Treatment of CHI

So far, there is no previous clinical experience with dasiglucagon SC infusion for the treatment of CHI. The following anticipated risks are derived from other clinical trials with dasiglucagon conducted in other indications, from marketed glucagon labelling information, and from native glucagon's physiological effects.

In clinical trials with dasiglucagon conducted up to now, the most frequent treatment-related AEs were nausea and vomiting, followed by headache.

Glucagon exerts positive inotropic and chronotropic effects and may, therefore, cause tachycardia and hypertension. Transient increases in heart rate and hypertension have been observed in clinical trials with dasiglucagon. Additionally, several episodes of hypotension and bradycardia have been noted in the clinical program, often in association with nausea and/or vomiting.

Accidental overdose may occur due to inappropriate handling of the infusion pump or due to pump malfunction. Overdose may result in nausea, vomiting, inhibition of GI tract motility, short-term increase in heart rate or blood pressure, and/or hypokalemia. Symptomatic care for nausea and vomiting, as well as monitoring of heart rate, blood pressure, and hypokalemia is advised.

Injection site reactions are seen with many injectable peptides. Injection site reactions have been reported across trials, with similar frequency in all treatment groups (dasiglucagon, marketed

glucagons, and placebo), irrespective of dose. The injection site reactions were generally mild and transient.

Overall, the clinical trial data indicate that dasiglucagon has a low risk for induction of ADAs. Out of more than 350 doses of dasiglucagon administered to more than 200 patients, only 1 low-titer transient ADA incident has been reported to date, in a patient following administration of 11 SC doses of dasiglucagon or Lilly Glucagon ranging from 0.03 to 0.6 mg, with low binding and low *in vitro* neutralizing capability. No apparent clinical effects on PK, PD, or AEs were noted. Due to the crossover trial design, the ADA induction could not be ascribed to a specific treatment. Based on the current clinical experience and the product characteristics, the risk of dasiglucagon inducing an ADA response is considered low.

Administration of glucagon or dasiglucagon may be associated with a risk of allergic reactions similar to those observed for other therapeutic peptides or proteins.

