9.2.3. Randomization Exclusion Criteria

A screened patient will not be randomized if:

1. Mean IV glucose requirement is <10 mg/kg/min to maintain glycemia above 70 mg/dL (3.9 mmol/L) during the previous 24 hours prior to randomization
2. Use of glucagon within 24 hours before randomization.
3. Use of additional enteral glucose within 24 hours before randomization. Patients should be transitioned to IV glucose infusions only at least 24 hours before randomization.
4. Is not sufficiently clinically stable on IV GIR only (\pm diazoxide, as applicable), in the opinion of the investigator, to undergo the placebo-controlled randomized Part 1 of the trial (2x48 hours).

The Randomization Visit may be rescheduled once if Randomization Exclusion Criterion 2 is met.

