11.2.3.2. Clinical Examinations

Vital Signs

Vital signs, including blood pressure, heart rate, respiratory rate, and SpO₂ will be measured while the child is sleeping or in a calm state at times specified in the Schedule of Events (Section 18.1). Vital signs can be performed using the bedside monitoring device as per standard of care.

Twelve-lead Electrocardiogram

A standard 12-lead ECG will be performed while the child is sleeping or in a calm state at times specified in the Schedule of Events (Section 18.1). If it is not practical or possible, then a 2-lead ECG may be used.²⁴ If arrhythmia is detected on a 2-lead ECG, this should be followed by

12-lead ECG. All ECG recordings will be identified with the patient number, date, and time of the recording and will be attached to his or her medical record.

The ECG parameters (heart rate, PQ, QRS, QT, and QTcF) and any abnormality will be recorded and described in the eCRF, including the investigator's assessment of clinical significance (Abnormal, Clinically Significant; or Abnormal, Not Clinically Significant). At subsequent visits, any clinically significant deterioration of a pre-existing condition, as well as any new clinically significant findings, will be recorded as AEs.

Echocardiogram

An echocardiogram will be performed according to the time points specified in the Schedule of Events (Section 18.1).

Physical Examination and Neurological Examination

A complete physical examination of body systems according to standard of care and an age-appropriate neurological examination will be performed according to the Schedule of Events (Section 18.1).

Local Tolerability

Local tolerability data will be collected separately from AEs. Within the eCRF, data will be collected on the nature of any reaction (erythema, pain, swelling, etc.), the severity (mild, moderate, or severe), and any action taken (e.g., no action, interruption of infusion). The likely cause of the reaction will also be collected (e.g., insertion site, drug, adhesive dressing).

Other skin findings will be collected along other AEs. If clinical suspicion of NME is made, data describing the lesion(s) will be collected as an AE of special interest (AESI) (see Section 12.1.8), together with a photograph or series of photographs of the lesion(s) uploaded to a central repository.

Assessment of Fluid Balance for Patients Receiving IV Glucose

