- b After screening, eligible patients will complete a minimum 24-hour run-in period to confirm the IV glucose randomization requirement (≥ 10 mg/kg/min). All non-nutritional carbohydrates and carbohydrate fortification of feeds are prohibited during this 24-hour run-in period.
- c Visits 5 (Day 11) and 6 (Day 18) can be converted to phone visits at the investigator's discretion.
- d Patients who are discharged from the hospital before Day 25 will be contacted by the investigator by telephone the day after discharge. The investigator will ask the parent(s)/guardian if they have any questions about the trial procedures and if their child has experienced any AEs.
- e Body length will be measured at screening and at the End of Treatment Visit.
- f For CHI diagnosis: Data on biochemical parameters, genotyping results, and information about PET CT should be captured when available.
- g An echocardiogram performed within 1 month of screening can be used.
- h Vital signs should be measured at 6 ± 1 , 12 ± 2 , and 24 ± 4 hours after initiation of the trial drug and every 8 ± 2 hours hereafter.
- i Fluid balance assessments are to be performed and documented every 8 hours as long as the patient is receiving IV glucose.
- j Clinical laboratory tests include hematology and biochemistry.
- k Blood test for anti-drug antibodies to be performed prior to dosing. Any anti-dasiglucagon antibody-positive patient (treatment induced or treatment boosted) will be monitored at an additional Follow-up Visit preferably 16 weeks after last ADA-positive sample. Patients completing the trial before the ADA screening and confirmatory assays have been approved by the FDA and who do not continue treatment in the long-term extension trial will have this additional visit 16 weeks after the end of trial visit (visit 8).

- 1 Sampling for drug exposure at Day 5 is only applicable for patients with a body weight of ≥ 4 kg. This sample should only be collected if it does not compromise the total amount of blood drawn according to Section 11.2.3.1.
- m The diary should be dispensed if a patient is discharged from the hospital during Part 2. At subsequent visits, the parent(s)/guardian will return the completed diary and obtain a new one.

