6.1.1.2. Safety

For safety endpoints, baseline is defined as the last observation recorded prior to the first dose (Placebo or Dasiglucagon) on Day 1.

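### The vital-signs schedule has no pre-dose Day 1 reading, so the default blood-pressure and heart-rate baseline is a screening value 1 to 28 days old that may have been taken on marketed glucagon

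*Protocol*

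**What the plan says.** **Baseline rule.** Protocol 13.4.4 states: "Baseline is defined as the last nonmissing assessment before the first exposure to trial drug in the trial". SAP 6.1.1.2 gives the same rule for safety endpoints: "baseline is defined as the last observation recorded prior to the first dose (Placebo or Dasiglucagon) on Day 1". SAP 6.1.5, Table 3, gives Baseline a window of Day -28 to Day -1 and gives Day 1 a window of its own.

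**Timing of vital signs.** Protocol 11.2.3.2 leaves timing to the Schedule of Events: vital signs "will be measured while the child is sleeping or in a calm state at times specified in the Schedule of Events". That table has one entry at Screening (Day -28 to -1) and then entries for Days 1 to 6 under footnote h. Footnote h puts readings at 6±1, 12±2 and 24±4 "hours after initiation of the trial drug and every" 8±2 hours from then on. Both protocol versions (13.0 and 14.0) and SAP Table 2 carry the same footnote.

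**Glucagon before the trial.** Protocol 9.2.3 bars randomization after "Use of glucagon within 24 hours before randomization", and 10.11.2 prohibits marketed glucagon from the same point. Neither restricts it earlier in screening. Section 6.2 says it is often used in the diagnostic phase of the disease. Section 6.3.6 says: "Glucagon exerts positive inotropic and chronotropic effects and may, therefore, cause tachycardia and hypertension".

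**Use of the baseline.** Protocol 13.4.4.3 and SAP 9.3 call for change from baseline in blood pressure and heart rate, and for shift tables.

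**The concern.** A change-from-baseline table for a drug with expected haemodynamic effects needs a reference taken shortly before dosing and off any drug of the same class. The scheduled reference guarantees neither. It can be four weeks old in an infant who may have been 7 days of age when it was taken. It can also come from a time when the child was on marketed glucagon. In such a child the baseline may already contain the class effect, so a rise on dasiglucagon would look smaller than it is. In a child not on glucagon, the difficulty is an old reading, and the direction of any error is unknown.

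Safety and tolerability form the secondary objective, and blood-pressure and heart-rate change is listed among the events of special interest (Protocol 12.1.8). A usable baseline is therefore worth having even though the analysis is descriptive.

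**Working it through.** **1. The screening window.** Protocol 11.1 gives a maximum duration of 81 days. Its parts are 28 (screening) + 4 (Part 1) + 21 (Part 2) + 28 (follow-up) = 81, which reproduces the figure and confirms that the full 28-day screening period is intended.

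**2. Age of the default baseline.** The schedule runs from Day -1 directly to Day 1, with no Day 0. A Day -28 reading is 28 days old at first dose and a Day -1 reading is 1 day old. The range is 1 to 28 days. A child screened at the minimum age of 7 days could be 7 + 28 = 35 days old at first dose.

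**3. First scheduled reading after Screening.** 6 - 1 = 5 hours to 6 + 1 = 7 hours after trial drug starts. With uninterrupted escalation under Protocol 10.2 (10 µg/hr at the start, plus 10 every 2 hours), the rate is 30 µg/hr at 4 hours and 40 µg/hr at 6 hours. In the dasiglucagon period the first reading is thus well into titration and cannot serve as a baseline.

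**4. Is the omission only apparent?** In the same table, footnote k marks the Day 1 antibody sample as pre-dose. Pre-dose timing was written down where it was intended, and footnote h has none.

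**5. Would an unscheduled pre-dose reading be used?** SAP 6.1.1.2 would take it, being the last value before first dose. SAP 6.1.5 admits an unscheduled value only when no scheduled one is available and it falls inside the visit window. A Day 1 value falls in the Day 1 window, not in Baseline, and scheduled Screening and Day 1 values would normally exist. The two SAP rules conflict, so such a reading cannot be relied on.

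**6. Which tables are affected.** Let *g* be any glucagon effect present at screening, *t* the drift since screening, and *d* the dasiglucagon effect. Then, approximately:

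- change from baseline on dasiglucagon = *d* + *t* - *g*
- change from baseline on placebo = *t* - *g*
- dasiglucagon minus placebo in Part 1 = *d*

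The baseline terms cancel in the Part 1 contrast, apart from any drift between the two 48-hour periods. They do not cancel in Part 2, where the reported change is *d* + *t* - *g* with no concurrent control. The documents give no value for *g* or *t*, so the size cannot be computed.

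**The case against.** The strongest reply is that pre-dose vital signs may exist already. Protocol 11.2.3.2 requires a documented fluid balance assessment at least every 8 hours in any inpatient on IV glucose, and vital signs are among its elements. Every eligible child needs continuous IV glucose. Eligibility, which includes the absence of hypertension and hypotension, is also rechecked on Day 1. This stands in part: a site may well have a value. But these checks are not scheduled as vital-sign records before Day 1, nothing says they enter the vital-signs dataset, and neither document names them as baseline.

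A second reply is that the analysis is descriptive, in 12 patients who each have a placebo period. That stands, and it limits the importance of the point.

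Some stronger readings are tempting, but the documents do not support them:

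- *That baseline is the only reference in Part 2.* Each child who completes Part 1 has placebo readings ending 0 to 2 days before Part 2, and actual values are summarized by treatment and part.
- *That octreotide at screening distorts the baseline in the same way.* The protocol describes no effect of octreotide on heart rate or blood pressure.
- *That capture of the event of special interest depends on this baseline.* It rests on clinical significance, and no numeric change from baseline triggers it.
- *That the Day 1 ECG should be declared pre-dose.* Day 1 has a single untimed ECG, and Protocol 8.1 has safety assessments made daily after trial drug starts. Relabelling could remove the only scheduled Day 1 on-drug ECG.

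**Conclusion.** The point holds as a gap in scheduling and baseline definition. Followed as written, the plan gives all 12 infants a default vital-sign baseline 1 to 28 days old, possibly on marketed glucagon. The consequence is confined to the descriptive change-from-baseline and shift tables, chiefly in Part 2. The efficacy analyses are untouched.

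This conclusion assumes that sites record vital signs as scheduled and that the fluid balance checks do not feed the vital-signs dataset. If they do, a fresher value may exist, but SAP 6.1.5 still leaves its use unclear. A reader might infer that vital-sign changes on dasiglucagon are known to be understated. The documents do not show that: glucagon at screening is permitted, not required, the number of children on it is unknown, and Protocol 6.3.6 also reports hypotension and bradycardia with dasiglucagon. The case for acting is that the remedy is very cheap and gives the planned tables a better reference.

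**What to change.** 1. In the Schedule of Events of both protocol versions and in SAP Table 2, add one timed Day 1 vital-sign record, after the run-in and before trial drug starts. Protocol 11.2.3.2 already provides the means: "Vital signs can be performed using the bedside monitoring device as per standard of care".
2. In Protocol 13.4.4 and SAP 6.1.1.2, name this record as the vital-sign baseline, with the latest earlier value used only if it is missing.
3. In SAP Table 3, let a pre-dose Day 1 value fall in the Baseline window, so that 6.1.5 and 6.1.1.2 no longer conflict.
4. For the Day 1 ECG, record its time relative to first dose and classify it as baseline or on-treatment accordingly. Do not relabel it as pre-dose.

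The cost is one extra eCRF line per patient (12 in all), a time field for the Day 1 ECG where none is recorded, and the wording changes. No blood, device or dosing change is involved.

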13.4.4.1. Adverse Events

Adverse events will be coded using the most current version of MedDRA.

A treatment-emergent AE is defined as an AE with an onset at the time of or following the start of treatment with the trial drug through the Follow-up Visit or Early Termination Visit, whichever occurs first.

The number and percentage of patients with AEs, as well as the number of AEs, will be displayed by system organ class, PT, and treatment group. The incidence of AEs will also be presented by severity and relationship to the trial drug. Serious AEs, AESIs and AEs resulting in discontinuation of trial drug will be summarized separately in a similar manner. Patient listings of AEs, SAEs, AESIs, and AEs causing discontinuation of trial drug and withdrawal from the trial will be produced.

13.4.4.2. Clinical Laboratory Evaluations

Descriptive summaries (mean, SD, median, minimum, and maximum) of actual (absolute) values and changes from baseline values will be presented for clinical laboratory values.

The number of patients with clinical laboratory values categorized as below, within, or above normal ranges will be tabulated showing change from baseline (shift tables) for each clinical laboratory analyte.

Laboratory values that are outside the normal range will also be flagged in the data listings, along with corresponding normal ranges. Any out-of-range values that are identified by the investigator as being clinically significant will also be shown in a data listing.

13.4.4.3. Vital Signs

Descriptive summaries (mean, SD, median, minimum, and maximum) of actual values and changes from baseline will be calculated for systolic blood pressure, diastolic blood pressure, heart rate, respiratory rate, and SpO₂.

The number of patients with vital signs values categorized as Abnormal, Clinically Significant or Abnormal, Not Clinically Significant will be tabulated showing change from baseline (shift tables) for each parameter.

